1.4 RATIONALE FOR TREATMENT SCHEDULES

We selected rivaroxaban 2.5mg twice daily because:

1. Rivaroxaban is the only FXa inhibitor that has shown to improve cardio-vascular outcomes in patients with¹ and without ACS^{2, 3}; furthermore, it has shown to reduce systemic non-CNS systemic⁴ embolism and stent thrombosis post PTA⁵.
2. A 2.5 mg twice daily dose appears to provide the best risk/ratio in combination with antiplatelet agents for the prevention of vascular events in patients treated with antiplatelet agents. The risk of bleeding in patients receiving rivaroxaban and antiplatelet appears to be increased regardless of the treatment indication. Mega et al suggested that a 10 mg daily dose of Rivaroxaban in combination with aspirin was associated with a 2.2% risk of TIMI major bleeding whereas it was 0% in those treated with a 5 mg daily dose plus aspirin. In participants treated with a total daily dose 5 mg of rivaroxaban, those who received 2.5 mg twice daily had a lower bleeding risk than those treated with 5 mg once daily (1.4 vs. 2.9%); furthermore twice daily dosing was associated with a lower number of cardiovascular events (6.6 vs. 9.4%)(6). In ATLAS ACS 2–TIMI 51, the 2.5-mg twice-daily dose of rivaroxaban compared with placebo was associated with reductions of 34% for cardiovascular death and 32% for all-cause death, which were not seen with the 5-mg twice-daily dose(1).
3. Although previous studies looking at the role of anticoagulation post PTA for CLI have used prophylactic doses of LMWH(7), our concern is that patients with CLI are older and sicker and a dose of rivaroxaban of 10 mg once daily in combination with aspirin will be associated with a higher bleeding risk without significant improvement in outcomes.

We selected ASA-clopidogrel as comparator because it is the treatment recommended by guidelines^{7,8}, and is used by 50% of vascular surgeons in Canada

Since optimal medical management to decrease restenosis and thrombosis rates following PTA would make an important contribution to the sustained success of endovascular treatment, the proposed study will evaluate indicators of the effect of rivaroxaban in patients with CLI requiring PTA.

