8.1.2 Secondary Outcomes

1. Clinical improvement defined as cumulative improvement of 2 classes of the Rutherford scale without the need for repeated TLR in surviving patients.
2. Event-free survival
3. Overall survival
4. Target lesion revascularization (TLR) between day 1 and final visit
5. Target vessel revascularization (TVR) between day 1 and final visit
6. Peri-procedure death within 30 days
7. Cumulative rate of major adverse cardiovascular events (as defined in 8.1.2.1) between day 1 and final visit
8. Cumulative rate of major bleeding (as defined in 8.1.2.2) between day 1 and day 90.
9. Cumulative rate of minor bleeding (as defined in 8.1.2.2) between day 1 and day 90
10. Biological plausibility by measuring coagulation changes and SMC proliferation markers within 7 and 90 days based on the following markers: D-dimer, soluble CD40/44 ligands, and ERK 1/2.
11. Patency rates based on the ABI index and with an ultrasound at 6 and 12 months
12. Information about feasibility of a future study:
 - a. The total number of eligible candidates identified;

- b. The percentage of eligible patients referred to our study;
- c. The percentage of eligible patients who consent to be enrolled

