8.1.2.2 BLEEDING

Bleeding will be classified as per the Thrombolysis in Myocardial Infarction (TIMI) bleeding classification scheme:

Major Bleeding:

- Any intracranial bleeding
- Clinically significant overt signs of bleeding associated with a drop in hemoglobin of > 50 g/L (or, when hemoglobin is not available, an absolute drop in hematocrit of > 15%),
- Fatal bleeding that directly results in death within 7 days.

Minor Bleeding:

- Any clinically overt sign of bleeding (including imaging) that is associated with a fall in hemoglobin of 30 to 50 g/L (or, when hemoglobin is not available, a fall in hematocrit of 9 to 15%).
- Any overt sign of hemorrhage that meets one of the following criteria and does not meet criteria for a major or minor bleeding event, as defined above
 - Requiring intervention (medical practitioner-guided medical or surgical treatment to stop or treat bleeding, including temporarily or permanently discontinuing or changing the dose of a medication or study drug)
 - Leading to or prolonging hospitalization
 - Prompting evaluation (leading to an unscheduled visit to a healthcare professional and diagnostic testing, either laboratory or imaging)

Minimal Bleeding:

- Any overt bleeding event that does not meet the criteria for major or minor bleeding listed above
- Any clinically overt sign of bleeding (including imaging) that is associated with a fall in hemoglobin < 30 g/L (or, when hemoglobin is not available, a fall in hematocrit of < 9%).

Bleeding will be further identified using the following criteria:

- Significant: major bleeding or minor bleeding requiring medical attention.
- Instrumented: any bleeding that occurs as a result of an invasive procedure.
- Spontaneous: any bleeding that is not the direct result of an invasive procedure (e.g. gingival bleeding, epistaxis, gastrointestinal bleeding).

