8.2 SAMPLE SIZE CALCULATION

Based on recent data published by Conte et al² we expect that during 1 year of follow up, 54% of participants will experience the primary outcome. A total sample of 40 participants was selected and is within the recommended approach for pilot studies evaluating effects when no prior information upon which to base the sample size is available. This sample size will allow us to detect an absolute 20% reduction in the main clinical outcome with a single sided alpha of 0.2 and power of 0.6 as recommended for pilots studies⁵⁹⁻⁶¹. The study will be considered successful if we can demonstrate a reduction in events in the intervention group supported by changes in biomarkers levels (biological plausibility).

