8.3 STATISTICAL ANALYSIS

All the continuous outcomes will be evaluated with the paired T-test or Wilcoxon-rank sum; proportions will be evaluated using the Fisher's exact test.

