9.3 STEERING COMMITTEE

A Steering Committee comprised of the trial's co-investigators will manage the overall conduct of the trial. Drs. [name], [name] and [name] will regularly review the progress of the trial. The Steering Committee will review how the trial was conducted and review the various outcomes of the trial to determine if the evidence justifies a full randomized trial.

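### Bleeding is to be compared by Fisher's exact test alone; at about 20 participants per arm, a risk difference with a 95% interval should be planned as well

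*Combined protocol and SAP*

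**What the plan says.** Section 8.1.2 lists two bleeding outcomes. Item 8 is "Cumulative rate of major bleeding (as defined in 8.1.2.2) between day 1 and day 90" and item 9 is "Cumulative rate of minor bleeding (as defined in 8.1.2.2) between day 1 and day 90".

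Section 8.1.2.2 grades each bleed as major, minor or minimal on the TIMI scheme and then adds further descriptors. One of these is "Significant: major bleeding or minor bleeding requiring medical attention". That category does not appear among the 12 secondary outcomes in 8.1.2.

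Section 8.3 is a single sentence. For binary outcomes it says that "proportions will be evaluated using the Fisher's exact test". It does not name bleeding; the test applies to items 8 and 9 through this general rule. No risk difference, risk ratio or confidence interval is planned anywhere in the document, for bleeding or for any other outcome.

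On size, section 8.2 says "A total sample of 40 participants was selected". It gives no expected bleeding rate, level or power for bleeding. Under section 9.3 the steering committee will "review the various outcomes of the trial to determine if the evidence justifies a full randomized trial".

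**The concern.** Bleeding is the main harm that the protocol itself names for this combination. Section 1.4 says "The risk of bleeding in patients receiving rivaroxaban and antiplatelet appears to be increased regardless of the treatment indication", and the dose was chosen largely on bleeding grounds. The review in 9.3 therefore needs to know how large a bleeding excess on rivaroxaban is still compatible with the data. A significance test on a handful of events does not answer that. A large p-value can be read as no difference when a substantial excess remains possible. An interval for the risk difference states directly what has not been excluded.

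There is also a smaller gap. One participant can have both a major and a minor bleed, so the two separate rates do not show how many participants bled.

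**Working it through.** **The plan's own figure.** There is none for bleeding. The one design statement, in 8.2, concerns the primary outcome: 54% against 34%, one-sided alpha 0.2, power 0.6. At 20 per arm the pooled normal approximation gives power 0.67 and a one-sided Fisher test gives 0.57, on either side of the stated 0.6. The bleeding point does not depend on this.

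**Inputs.**
- Total of 40 (section 8.2); 20 per arm is an assumption, because no allocation ratio is stated.
- Bleeding counts are assumptions, because no rate is given for this trial. Section 1.4 quotes bleeding figures between 0% and 2.9% for rivaroxaban regimens in another population, and not all are labelled major. As an order of magnitude only, 20 × 0.029 = 0.58 participants per arm. No figure is given for minor bleeding.
- Sidedness and level for bleeding are not stated, so both p-values are shown.

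**Fisher's exact test, 2 of 20 v 1 of 20.** With 3 bleeders among 40, the probability that k are in the rivaroxaban arm is C(20,k) × C(20,3-k) / C(40,3), where C(40,3) = 9880.
- k = 3: 1140/9880 = 0.115
- k = 2: 190 × 20/9880 = 0.385
- k = 1: 0.385
- k = 0: 0.115

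One-sided p (rivaroxaban higher) = 0.385 + 0.115 = 0.50. No split is more probable than the one observed, so two-sided p = 1.00.

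**Newcombe interval, same table.** The Wilson limits for each arm are [p + z²/2n ± z√(p(1-p)/n + z²/4n²)] / (1 + z²/n), with z = 1.96 and n = 20.
- 2/20: 0.0279 to 0.3010
- 1/20: 0.0089 to 0.2361
- Difference: 0.10 - 0.05 = 0.05
- Lower limit: 0.05 - √[(0.10 - 0.0279)² + (0.2361 - 0.05)²] = 0.05 - 0.1996 = -0.150
- Upper limit: 0.05 + √[(0.3010 - 0.10)² + (0.05 - 0.0089)²] = 0.05 + 0.2052 = +0.255

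**Other sparse tables, by the same formulas (20 per arm).**

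| Rivaroxaban v clopidogrel | Fisher p, two-sided | Fisher p, one-sided | Risk difference, points (95% CI) |
|---|---|---|---|
| 0 v 0 | 1.00 | 1.00 | 0 (-16.1 to +16.1) |
| 1 v 0 | 1.00 | 0.50 | +5 (-11.6 to +23.6) |
| 1 v 1 | 1.00 | 0.76 | 0 (-19.1 to +19.1) |
| 2 v 1 | 1.00 | 0.50 | +5 (-15.0 to +25.5) |
| 2 v 2 | 1.00 | 0.70 | 0 (-21.4 to +21.4) |
| 4 v 2 | 0.66 | 0.33 | +10 (-13.4 to +32.8) |

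In every row the upper limit is at least 16 points, and neither p-value conveys this.

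**Overlap of items 8 and 9.** If a participants have a major bleed and b have a minor bleed, the number with at least one lies between max(a, b) and a + b. The two rates alone do not fix it.

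**The case against.** The strongest reply is that the planned output is more than a p-value. Items 8 and 9 are rates, so a figure per arm will exist. A reader who sees 2 of 20 against 1 of 20 sees how sparse the data are and can compute every interval above. This stands in part: the imprecision would not be hidden. It remains true that the plan commits to no between-arm estimate or interval, and that the test it does commit to is the least informative summary at this size.

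Some stronger readings are tempting, but the documents do not support them:
- *A non-significant bleeding test would be taken as evidence of safety.* No stated decision uses a bleeding p-value. The success criterion in 8.2 concerns fewer events together with biomarker changes, and 9.3 sets no threshold.
- *Fisher's test returns the same p = 1.00 for quite different tables, and 5 v 0 is needed for significance.* Both hold only for a two-sided test, and the second also needs a 5% level (5 v 0 gives 0.047, 4 v 0 gives 0.106). The only alpha stated is one-sided 0.2, for the primary outcome; on that basis the p-values in the table differ and 3 v 0 already crosses (p = 0.115).
- *The quoted 1.4% and 2.9% predict how many major bleeds will occur.* Section 1.4 does not label them as major bleeding, they come from another population, and 2.9% belongs to a once-daily regimen not used here.
- *Leaving the Significant category out of 8.1.2 is an error.* Reporting TIMI tiers separately is a legitimate choice, and the category is to be recorded for each bleed anyway, so a count can be tabulated. A pooled outcome is largely a preference.

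It is also fair to say that bleeding is not unique: 8.3 plans no interval for any outcome. That argues for a general sentence, not against the point. The adverse event tables in 9.4 and the unspecified treatment comparisons in 9.5.1 serve the DSMB and do not supply a planned estimate.

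**Conclusion.** The point holds as a low-cost improvement to section 8.3. The only planned comparison of the day-90 bleeding rates is Fisher's exact test, by the general rule for proportions. With few events at about 20 per arm, that test says little about how large a bleeding excess remains possible. In the worked case of 2 v 1, an excess of about 25 points is not excluded; even with no bleeds in either arm, one of about 16 points is not.

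These sizes rest on 1:1 allocation, on assumed counts and on a 95% level. The p-values are illustrative, since the documents set neither sidedness nor level for bleeding. The imprecision itself comes from the sample of 40 and is not a fault of the test. Nothing here threatens the primary outcome.

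**What to change.** In section 8.3, add one sentence: each bleeding outcome will be reported as number and percentage of participants per arm, with the risk difference (rivaroxaban minus clopidogrel) and a Newcombe or exact 95% confidence interval; the Fisher p-value is optional. The same sentence can cover the other binary outcomes. It should state the denominator, including how participants who die or withdraw before day 90 are counted.

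Optional and descriptive: also tabulate participants with at least one Significant bleed, as already defined in 8.1.2.2. Items 8 and 9 stay as they are. That count includes milder bleeds, which are more open to reporting differences in an open-label trial, and blinded adjudication (9.5.4) cannot recover bleeds that were never reported. Major bleeding should therefore remain a separate outcome.

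The cost is one sentence and, if the option is taken, one table row. The bleeds are already to be graded and adjudicated, so no new visit, test or staff time is needed. The change adds no power.

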8.1.2.1 MAJOR ADVERSE CARDIOVASCULAR EVENTS (MACE)

Any of the following events during follow up

1. Ischemic Stroke
	
Sudden onset of a neurological deficit that persists for more than 24 hours and involves one or more of the following:
 
 a) Hemiparesis: involving the face, arm and/or leg unilaterally b) Hemisensory loss; involving face, arm and/or leg unilaterally c) Speech impairment; (ie. Aphasia) d) Visuo-spatial impairment e) Visual loss (monocular or binocular) f) Two or more of the following symptoms which suggest vertebrobasilar involvement: 
 i. incoordination/ataxia ii. cranial nerve abnormality iii. dysarthria iv. dysphagia v. vertigo vi. reduction/loss of consciousness vii. diplopia g) Objective and persistent (more than one week) worsening of a previous deficit or worsening associated with an appropriate new finding on CT scan or MRI.

2. Transient Ischemic Attack
	
A transient ischemic attack is defined for the purposes of this trial as a sudden onset of a neurological deficit lasting at least one minute but less than 24 hours. (Isolated syncope will not be considered a TIA unless this occurs with one or more of the following neurological symptoms suggesting vertebrobasilar involvement.
 
 a) Hemiparesis; involving face, arm and/or leg unilaterally b) Hemisensory loss; involving face, arm and/or leg unilaterally c) Speech impairment; (ie. Aphasia) d) Visuo-spatial impairment e) Visual Loss (monocular or binocular) f) Two or more of the following symptoms: 
 i. Incoordination/ataxia, ii. Cranial nerve abnormality, iii. Dysarthria, iv. Dysphasia, v. Vertigo, vi. Reduction/loss of consciousness, vii. Diplopia

3. Myocardial Infarction	At least two of: a) Ischemic chest pain, b) EKG changes compatible with a MI(hyper acute T wave, elevated ST segment, T wave inversion, presence of new bundle branch block, loss of R wave height, development of Q waves) or c) elevation of cardiac enzymes (troponin, CK, CKMB isoenzyme, or other cardiac enzymes) to at least 2X the upper limit of the normal reference range or 3X the upper limit of normal within 48 hours after percutaneous coronary intervention (or if markers are already elevated, greater than 50% of the lowest recovery level from the index infarction
4. Vascular Death	Cardiac or cerebrovascular death excluding subarachnoid or primary intracranial haemorrhage or fatal pulmonary embolism.

8.1.2.2 BLEEDING

Bleeding will be classified as per the Thrombolysis in Myocardial Infarction (TIMI) bleeding classification scheme:

Major Bleeding:

- Any intracranial bleeding
- Clinically significant overt signs of bleeding associated with a drop in hemoglobin of > 50 g/L (or, when hemoglobin is not available, an absolute drop in hematocrit of > 15%),
- Fatal bleeding that directly results in death within 7 days.

Minor Bleeding:

- Any clinically overt sign of bleeding (including imaging) that is associated with a fall in hemoglobin of 30 to 50 g/L (or, when hemoglobin is not available, a fall in hematocrit of 9 to 15%).
- Any overt sign of hemorrhage that meets one of the following criteria and does not meet criteria for a major or minor bleeding event, as defined above
 - Requiring intervention (medical practitioner-guided medical or surgical treatment to stop or treat bleeding, including temporarily or permanently discontinuing or changing the dose of a medication or study drug)
 - Leading to or prolonging hospitalization
 - Prompting evaluation (leading to an unscheduled visit to a healthcare professional and diagnostic testing, either laboratory or imaging)

Minimal Bleeding:

- Any overt bleeding event that does not meet the criteria for major or minor bleeding listed above
- Any clinically overt sign of bleeding (including imaging) that is associated with a fall in hemoglobin < 30 g/L (or, when hemoglobin is not available, a fall in hematocrit of < 9%).

Bleeding will be further identified using the following criteria:

- Significant: major bleeding or minor bleeding requiring medical attention.
- Instrumented: any bleeding that occurs as a result of an invasive procedure.
- Spontaneous: any bleeding that is not the direct result of an invasive procedure (e.g. gingival bleeding, epistaxis, gastrointestinal bleeding).

8.2 SAMPLE SIZE CALCULATION

Based on recent data published by Conte et al² we expect that during 1 year of follow up, 54% of participants will experience the primary outcome. A total sample of 40 participants was selected and is within the recommended approach for pilot studies evaluating effects when no prior information upon which to base the sample size is available. This sample size will allow us to detect an absolute 20% reduction in the main clinical outcome with a single sided alpha of 0.2 and power of 0.6 as recommended for pilots studies⁵⁹⁻⁶¹. The study will be considered successful if we can demonstrate a reduction in events in the intervention group supported by changes in biomarkers levels (biological plausibility).

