Design:	This is a pilot study conducted at one center, The Ottawa Hospital. It is a Phase 2 open label randomized controlled trial. Consenting participants, meeting all eligibility criteria will be randomized, post PTA procedure, to one of two groups: Rivaroxaban 2.5 mg BID X 90 days plus ASA 81 mg daily OR Clopidogrel 75 mg daily X 90 days plus ASA 81 mg daily Participants will have study drug dispensed at Day 1 and take medication for 90 days. ASA may be continued after the study, for both groups, as per the standard of care. Visits will occur at 7 days, 30 days, 90 days, 6 months and 12 months. Participants will be followed for 12 months (\pm 14 days) in total. Adverse events will be collected for the first 90 days .
Intervention Description:	Treatment Arm 1 Rivaroxaban 2.5 mg twice daily for 90 days (rivaroxaban will be started 6 to 8 hours after the finalization of the procedure) and 325mg of ASA on day 1 then 81 mg of ASA daily for 89 days Treatment Arm 2 Clopidogrel 300mg on Day 1 (loading dose) then 75 mg daily for 89 days and 325mg of ASA on Day 1, then 81 mg of ASA daily for 89 days
Number of participants:	40

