1 STUDY RATIONALE AND BACKGROUND

1.1 CRITICAL LIMB ISCHEMIA (CLI)

Peripheral arterial disease (PAD) affects over 27 million people in the industrialized world, and is associated with significant morbidity and mortality¹. Up to 10% of patients with PAD² will develop critical limb ischemia (CLI) presenting as resting pain, ulcers, gangrene, and limb loss^{1;3;4}. The typical prognosis of CLI is poor. Within 3 months of onset, 12% of patients will require an amputation and 9% will die; by one year the mortality rate is 22%². With rates surpassing those of patients with coronary artery disease (CAD), patients with CLI are also at high risk of stroke, acute coronary syndrome (ACS), and cardiovascular (CV) death^{5;6}.

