8 STATISTIC ANALYSIS

8.1 STUDY OUTCOMES

8.1.1 Primary Outcome

The primary outcome is a combined endpoint consisting of any Rintervention , Above ankle amputation and Stenosis (RAS)²at one year The 3 components of RAS are defined as follows:

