11 ANTICIPATED RESULTS- DISSEMINATION PLAN

The results of our trial will be used by the investigators to evaluate the need for further studies evaluating the role of the addition of rivaroxaban to reduce clinically relevant outcomes in patients with CLI requiring PTA and will provide justification to external funding agencies before a commitment is made to fund a full trial.

Regardless of the results of the trial, we will make every effort to publish and present our data and conclusions about feasibility such that future researchers might benefit from this work.

The International Committee of Medical Journal Editors (ICMJE) member journals have adopted a trials-registration policy as a condition for publication. This policy requires that all clinical trials be registered in a public trials registry such as ClinicalTrials.gov*, which is sponsored by the National Library of Medicine. It is the responsibility of the QI to register this trial in an acceptable registry on or before patient enrollment.

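### One-sided Fisher at the stated alpha of 0.2 gives power of about 0.57 and a true alpha of about 0.13; Boschloo's exact test gives about 0.65 within 0.2 from the same 40 participants

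*Combined protocol and SAP*

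**What the plan says.** Section 8.2 expects 54% of participants to have the primary outcome, RAS, within one year. It continues: "A total sample of 40 participants was selected", a number said to be enough to "detect an absolute 20% reduction in the main clinical outcome with a single sided alpha of 0.2 and power of 0.6". It names no test and gives no numbers per arm.

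Section 8.3 gives the analysis in one sentence. On this point it says only that "proportions will be evaluated using the Fisher's exact test", without a side, a level or a named primary comparison.

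The synopsis says participants "will be randomized, post PTA procedure, to one of two groups", and Section 5.2 describes the web-based system. Neither gives an allocation ratio.

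Section 8.2 also has a success rule: "The study will be considered successful if we can demonstrate a reduction in events in the intervention group", with support from biomarker changes. It sets no threshold for either half. Section 11 adds that the results "will provide justification to external funding agencies before a commitment is made to fund a full trial".

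**The concern.** Fisher's test conditions on the total number of events, so with small arms few p-values are attainable and the true type I error can lie well below the nominal level. Unused alpha is lost power. An alpha and power quoted without a test may therefore not describe the test that is run. That matters here because alpha has deliberately been set high, at 0.2, to get usable power from 40 people.

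The success rule adds to this. If a reduction is not tied to the test, it could be taken as any lower observed event proportion, and the error rates in 8.2 would not describe that rule. The result is meant to inform whether a full trial is warranted, so the rule and its error rates should be fixed before the data are seen.

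**Working it through.** **Inputs.** From 8.2: N = 40, event rate 0.54, absolute reduction 0.20 (so 0.54 versus 0.34), one-sided alpha 0.2, stated power 0.6. From 8.3: Fisher's exact test. Assumed, because not stated: 20 per arm, 0.54 as the clopidogrel rate, no loss to follow-up.

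**1. The plan's own figure.** Pooled normal approximation:
- Mean rate (0.54 + 0.34)/2 = 0.44; null SE = √(2 × 0.44 × 0.56/20) = 0.157.
- Alternative SE = √[(0.54 × 0.46 + 0.34 × 0.66)/20] = 0.154.
- Power = Φ[(0.20 − 0.842 × 0.157)/0.154] = Φ(0.44) = 0.67.

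With a continuity correction the power is 0.546. The stated 0.6 lies between the two, and neither reproduces it exactly.

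**2. Fisher, one-sided at 0.2.** Let X be clopidogrel events and Y rivaroxaban events, independent binomials. Enumerate all 21 × 21 tables and reject when the one-sided hypergeometric p ≤ 0.2. Power is the sum of b(x; 20, 0.54) × b(y; 20, 0.34) over rejected tables. Size is the same sum at a common rate, maximised over that rate.

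**3. Boschloo, one-sided at 0.2.** This uses Fisher's p as the test statistic, but sets its cut-off so that the maximum size over the common rate stays within 0.2. At 20 per arm the cut-off is Fisher p ≤ 0.2616. Since that exceeds 0.2, every Fisher rejection is also a Boschloo rejection. For example, with 10 clopidogrel events, Fisher's p is 0.167 at 6 rivaroxaban events and 0.262 at 7. Fisher rejects at 6 or fewer, Boschloo at 7 or fewer.

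| Clopidogrel / rivaroxaban | Fisher power | Fisher max. size | Boschloo power | Boschloo max. size |
|---|---|---|---|---|
| 20 / 20 | 0.569 | 0.134 | 0.646 | 0.196 |
| 19 / 21 | 0.584 | 0.144 | 0.619 | 0.191 |
| 21 / 19 | 0.555 | 0.144 | 0.659 | 0.191 |
| 18 / 18 (10% loss, assumed) | 0.518 | 0.121 | 0.599 | 0.182 |

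At 20 per arm, Fisher's unused alpha is (0.200 − 0.134)/0.200 = 33%. Its shortfall in power is 0.600 − 0.569 = 0.031. Boschloo's gain is 0.646 − 0.569 = 0.077.

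**4. Sensitivity to the 54%.** If 54% is the rate over both arms (0.64 versus 0.44), Fisher's power is 0.568, so the conclusion does not change.

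**5. Success read as any lower observed proportion.** At 20 per arm with 0.54 in both arms, the chance of a tie is Σ b(k; 20, 0.54)² = 0.126. By symmetry the chance of fewer rivaroxaban events is (1 − 0.126)/2 = 0.437. With arms of 19 and 21 it is 0.485 to 0.515. Under 0.34 versus 0.54 at 20 per arm it is 0.872. None of these corresponds to alpha 0.2 and power 0.6.

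**The case against.** The strongest reply is that nothing here is wrong. Sections 8.2 and 8.3 are adjacent. The first gives the side and level, the second the test, and together they give power of 0.57, which rounds to the stated 0.6. Fisher is a valid choice for 40 participants, and being conservative does not make it invalid. Most of this stands, which is why the point concerns efficiency and clarity. What remains is that Boschloo dominates Fisher at the same level and sample size. The gain is specific to Boschloo: the exact unconditional test ordered by the pooled z statistic reaches only 0.573.

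A reader might go further in three ways that the documents do not support.

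- *That the power of 0.6 is an arithmetic error.* No test is named beside it, and the plausible methods fall on both sides of it.
- *That Fisher may be run two-sided, with much lower power.* Section 8.3 does not repeat the side, but the only side stated anywhere is one-sided.
- *That the trial's false-positive risk is 44%.* That figure covers only the clinical half of the success rule, on its loosest reading. The biomarker half could only lower it, by an amount that cannot be computed because it too has no threshold. The sentence directly follows the alpha and power statement, so the test is the more natural reading. Section 9.3 also has the Steering Committee review trial conduct and various outcomes, so a full trial does not hang on one result.

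**Conclusion.** The point holds as a modest inefficiency with some missing specification. Under the assumptions listed, one-sided Fisher at 0.2 has power of about 0.57 (0.55 to 0.58 when the arms are 19 and 21) and a true alpha of at most about 0.13 (0.14 for those splits). Boschloo has power of about 0.65 (0.62 to 0.66) with a true alpha of at most about 0.20. Section 8.2 makes no allowance for loss to follow-up. With 18 evaluable per arm, Boschloo roughly meets the stated 0.6 and Fisher falls to about 0.52. The success sentence needs a definition because its loosest reading behaves quite differently from the stated error rates.

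**What to change.** - **Section 8.3:** state that the primary comparison, RAS by 12 months, is one-sided at 0.2 and uses Boschloo's exact test.
- **Section 8.2, power:** state the allocation. If it is 20 per arm, give power of about 0.65 with a true alpha of at most about 0.20, falling to about 0.60 if 10% of participants are lost. Label the 54% as the control rate if that is what is meant.
- **If Fisher is kept:** state power of about 0.57 at a true alpha of about 0.13. Reaching at least 0.60 with Fisher would take 22 per arm (44 in all, power 0.613); 21 per arm gives 0.592.
- **Section 8.2, success sentence:** say that a reduction in events means rejection by this test at 0.2.

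The cost is wording in two sections, with no added participants, visits or data. The downside is that Boschloo gives up Fisher's margin below 0.2 and is less familiar to clinical readers. Fisher's p-value can be reported beside it.
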